2.12 UNBLINDING

In general, there should be no need to unblind the allocated treatment during the treatment phase. If some contraindication to statins develops after randomisation, the trial treatment can be stopped and all usual standard care given. Unblinding should be done only in those rare cases where the clinician believes that clinical management depends importantly upon knowledge of whether the patient is receiving statin or placebo. In those few cases when urgent unblinding is considered necessary, a 24-hour telephone service will be provided by the CTU and details provided in the Investigator's Study File and the Patient Alert Card. The caller will be told whether the patient is receiving statin or placebo. An unblinding report form will be completed by the person requesting the unblinding. Participation will not restart once unblinding has occurred.

In this trial, it is important that the CTU is contacted for unblinding as any request is likely to originate from emergency departments or hospital clinics needing to know the treatment allocation urgently. As most GPs and research surgery staff do not provide a 24-hour cover, for patient safety reasons, the CTU will provide a 24 hour on-call unblinding service.

2.13 OUTCOME MEASURES

Primary outcome: The primary outcome is self-reported 'muscle symptoms', defined as pain, weakness, tenderness, stiffness or cramp to the body of any intensity, recorded where the participant believes they are associated with the study medication; these are the symptoms most commonly reported by patients and are often the reasons for discontinuation. The primary outcome will be assessed by the mean difference in VAS scores (range 0 to 100) between treatment periods with the trial treatment and treatment periods with placebo, estimated via a linear mixed model.

Secondary outcomes: Secondary outcomes relating to participant belief about the cause of their muscle symptoms, the site of muscle symptoms, how the muscle symptoms affected the participant and information about any other symptoms will be collected on the last day of each two-month treatment period, using a questionnaire (Appendix 5). The other secondary outcomes are adherence

to medication, the participant's decision about statin treatment following the trial, and whether they found their own trial result helpful.

Specifically, secondary outcomes will be:

1. The proportion of patients with muscle symptoms during each two-month period who report that they believe their symptoms were caused by the study medication, comparing periods of IMP treatment with placebo.
2. Site of muscle symptoms (single or multiple; head and neck/upper limbs/lower limbs/trunk).
3. Among patients reporting muscle symptoms, the difference in mean VAS scores (range 0 to 100) for the following, comparing periods of IMP treatment with placebo:
 - a. General activity
 - b. Mood
 - c. Walking ability
 - d. Normal work (includes both work outside the home and housework)
 - e. Relations with other people
 - f. Sleep
 - g. Enjoyment of life
4. Other symptoms that the patient believes can be attributed to the study medication (grouped: musculoskeletal; gastrointestinal; respiratory; neurological; psychological; other).
5. Adherence to study medication as assessed by: (a) self-report and (b) counting pills remaining in returned packages, and the relationship between adherence and muscle symptoms.
6. Participant decision regarding future statin use and the relationship to their primary outcome.
7. Whether patients found their own trial result helpful in making the decision about future statin use.

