BACKGROUND: Statins are the most commonly prescribed treatment in the UK. Recently updated NICE guidelines have lowered the threshold for statin use to include all patients with a 10% or greater 10-year risk of cardiovascular disease. Previous randomised trials have established the prevalence of serious adverse effects of statins such as rhabdomyolysis, however, many patients discontinue statins due to less severe symptoms, such as muscle pain or fatigue. Randomised trials have shown no differences between those taking statin and placebo in terms of the prevalence of these side effects (approximately 9%), but currently there is no pathway of care for clinicians to empirically and objectively evaluate whether symptoms reported by a statin-user are caused by the statin itself or the so-called 'nocebo' effect (symptoms reflecting patient expectation of side effects). Given the effectiveness of statins in preventing cardiovascular disease, accurate data on the cause of symptoms experienced during statin use are needed to reliably inform patient and clinician about continuation of use. The proposed StatinWISE trial will provide definitive answers to this important uncertainty about statin therapy.

AIM: To determine whether statins cause muscle symptoms.

PRIMARY OUTCOME: Patient reported muscle symptoms (pain, weakness, tenderness, stiffness or cramp).

SECONDARY OUTCOME: Relationship between individual trial result and patient decision whether to continue statins long term.

TRIAL DESIGN: A series of randomised, double-blinded N-of-1 trials.

DIAGNOSIS AND INCLUSION/EXCLUSION CRITERIA:

Inclusion criteria:

- Adults (aged 16 and over)
- Prescribed statin treatment in the last 3 years
- Stopped OR considering stopping statin treatment due to muscle symptoms
- Provided fully informed consent.

Exclusion criteria:

- Any previously documented serum alanine aminotransferase (ALT) levels at or above three times the upper limit of normal;

- Have persistent, generalised, unexplained muscle pain (whether associated or not with statin use) and have creatinine kinase (CK) levels greater than 5 times the upper limit of normal
- Any contraindications listed in the Summary of Product Characteristics for Atorvastatin 20 mg (Appendix 8)
- Should not be using atorvastatin 20mg daily in the opinion of the general practitioner.

TEST PRODUCT, REFERENCE THERAPY, DOSE AND MODE OF ADMINISTRATION: Once daily oral atorvastatin 20mg or placebo for 12 months.

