Appendix 4: StatinWISE Patient questionnaire

INSTRUCTIONS

This questionnaire is to be filled out once every two months (on day 56). We will remind you one day before it is due. Please answer all questions. If you need any help to complete the form. Please call our Freephone number [name] or email the study team: [contact].

PART 1: ADHERENCE TO MEDICATION

Step 1 (all participants):

Q1. How would you best describe your use of study medication in the past two months? (Please choose one of the following options)

- I didn't take my study medication at all
- I took my study medication on some days
- I took my study medication on most days, but missed an occasional dose
- I took my study medications every day

Step 2 (appears if the participant chooses "I didn't take my study medication at all", or "I took my study medication on some days"):

Q2. What was the reason that you didn't take your study medication every day in the past two months? (please tick all that apply)

- I forgot to take my study medication

Ticking the above will prompt the following option, if ticked, the trial team will action:

- Would you like a daily reminder sent to you via email/push notification

- I was prescribed another medication and my doctor told me to stop taking my study medication

Ticking the above will prompt an alert for the trial team to contact surgery for details and consider withdrawal from study

- My doctor recommended that I stop taking study medication because of muscle symptoms

Ticking the above will prompt an alert for the trial team to contact surgery for details

- I decided to stop taking study medication because of muscle symptoms

Ticking the above will prompt an alert for the patient to contact the GP for advice

- I didn't want to take my study medication

Ticking the above will prompt the following option, if ticked NO, the trial team will arrange for end of trial:

Do you still wish to participate in the trial: Yes No

- Other (please specify)

(free text)

PART 2: EXPLORING SYMPTOMS IN THE PAST TWO MONTHS

1. *(all participants):* In the last two months, have you experienced muscle symptoms, e.g. muscle pain or weakness?

Yes
 No

2. *(appears if the participant ticks yes for Question 1):* Do you think these muscle symptoms are related to your study medication?

Yes
 No
 Don't know

[figure not shown]
3. *(appears if the participant ticks no for Question 2):* What do you think may have caused these muscle symptoms?
(free text)

Don't know

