Appendix 5: StatinWISE VAS Pain Scale data form

You will be asked to complete this form each day during the last seven days of each two-month treatment period.

Day	Daily symptoms report		
1	1. Did you take study medication yesterday? No  Yes 	2. Did you experience muscle symptoms today? No  Yes  If yes:	3: Please indicate severity of muscle symptoms you experienced today.  0 No symptoms 5 Moderate symptoms 10 Worst possible symptoms
2	1. Did you take study medication yesterday? No  Yes 	2. Did you experience muscle symptoms today? No  Yes  If yes:	3: Please indicate severity of muscle symptoms you experienced today.  0 No symptoms 5 Moderate symptoms 10 Worst possible symptoms
3	1. Did you take study medication yesterday? No  Yes 	2. Did you experience muscle symptoms today? No  Yes  If yes:	3: Please indicate severity of muscle symptoms you experienced today.  0 No symptoms 5 Moderate symptoms 10 Worst possible symptoms

4	
1. Did you take study medication yesterday? No  Yes 
 
2. Did you experience muscle symptoms today? No  Yes  If yes:
 
3: Please indicate severity of muscle symptoms you experienced today.
 
5	
1. Did you take study medication yesterday? No  Yes 
 
2. Did you experience muscle symptoms today? No  Yes  If yes:
 
3: Please indicate severity of muscle symptoms you experienced today.
 
6	
1. Did you take study medication yesterday? No  Yes 
 
2. Did you experience muscle symptoms today? No  Yes  If yes:
 
3: Please indicate severity of muscle symptoms you experienced today.
 
7	
1. Did you take study medication yesterday? No  Yes 
 
If yes:
 
2. Did you experience muscle symptoms today? No  Yes  If yes:
 
3: Please indicate severity of muscle symptoms you experienced today.
 

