1.1 TRIAL SUMMARY

BACKGROUND: Statins are the most commonly prescribed treatment in the UK. Recently updated NICE guidelines have lowered the threshold for statin use to include all patients with a 10% or greater 10-year risk of cardiovascular disease. Previous randomised trials have established the prevalence of serious adverse effects of statins such as rhabdomyolysis, however many patients discontinue statins due to less severe symptomatic side effects, such as muscle pain or fatigue. Randomised trials have shown no differences between those taking statin and placebo in terms of the prevalence of these side effects (approximately 9%), but currently there is no pathway of care for clinicians to empirically and objectively evaluate whether symptoms reported by a statin-user are caused by the statin itself or the so-called 'nocebo' effect (symptoms reflecting patient expectation of side effects). Given the known effectiveness of statins in preventing cardiovascular disease, accurate data on the cause of symptoms experienced during statin use are needed to reliably inform patient and clinician about continuation of use. The proposed StatinWISE trial will provide definitive answers to this important uncertainty about statin therapy.

AIM: The StatinWISE trial will determine whether the muscle symptoms attributed to statin use by patients are caused by statins.

PRIMARY OUTCOME: Patient reported muscle symptoms (pain, weakness, tenderness, stiffness or cramp to the body) as measured by a visual analogue scale.

SECONDARY OUTCOMES:

- a) Whether or not the patient experiences muscle symptoms that they believe were caused by the study medication
- b) Site of muscle symptoms (single or multiple; head and neck/upper limbs/lower limbs/trunk)
- c) Visual analogue scale scores for the extent to which muscle symptoms affect:
 - a. General activity
 - b. Mood
 - c. Walking ability
 - d. Normal work (includes both work outside the home and housework)
 - e. Relations with other people
 - f. Sleep
 - g. Enjoyment of life
- d) Other symptoms that the patient believes can be attributed to the study medication (grouped: musculoskeletal, gastrointestinal, respiratory, neurological, psychological, other)
- e) Adherence to study medication as assessed by (i) self-report, and (ii) counting pills remaining in returned packages and the relationship between adherence and muscle symptoms

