1.7 DEFINITION OF PRIMARY OUTCOME

The primary outcome is patient reported muscle symptoms (pain, weakness, tenderness, stiffness or cramp to the body), on a Visual Analogue Scale (VAS), with possibly responses ranging from 0 to 10. This will be collected daily via the VAS Pain Scale data form (Appendix 1) during the last 7 days of each of the 6 treatment periods via the patient's nominated collection method (app, website, phone call, or paper form).

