2.3.8 CHANGES FROM TRIAL PROTOCOL

In the original protocol, the primary analysis model was exactly as above, but with fixed period effects in addition. These fixed effects have been removed, due to a strong belief that the clinical situation makes it unlikely for period effects to occur. The primary analysis model specified in the original protocol will be undertaken as a sensitivity analysis, as detailed in Section 2.3.4.

The original protocol did not mention one of the secondary analyses, which sets the primary outcome measure to zero if the patient attributes the symptoms to another cause (Section 2.3.2). This analysis was added after the protocol was finalised, but was included in the published protocol paper.

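### Protocol 2.13 restricts the primary outcome to symptoms the participant blames on the study medication; the rest of the Protocol, the daily form and the SAP do not, and SAP 2.3.8 does not declare the difference

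*Protocol*

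**What the plan says.** Protocol 2.13 gives the primary outcome as self-reported muscle symptoms of any intensity, "recorded where the participant believes they are associated with the study medication". It is assessed by the mean difference in VAS score between statin and placebo periods.

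The Protocol synopsis has no such limit: "Patient reported muscle symptoms (pain, weakness, tenderness, stiffness or cramp". Nor has the SAP. Section 1.1 adds only "as measured by a visual analogue scale", and section 1.7 reads "The primary outcome is patient reported muscle symptoms (pain, weakness, tenderness, stiffness or cramp to the body), on a Visual Analogue Scale (VAS".

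The daily form that generates the score (Protocol Appendix 5) asks "Did you experience muscle symptoms today" and then for severity. Attribution appears only in the Appendix 4 questionnaire: "Do you think these muscle symptoms are related to your study medication", with answers yes, no or don't know. Its instructions say "This questionnaire is to be filled out once every two months (on day 56".

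SAP 2.3.8 lists two changes from the protocol: removal of the fixed period effects, and an added attribution-based analysis. On the second it says: "The original protocol did not mention one of the secondary analyses, which sets the primary outcome measure to zero".

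**The concern.** Read literally, the 2.13 clause is a scoring rule: a symptom the participant puts down to gardening or arthritis would not count. That is a different outcome from all muscle symptoms under blinding. The trial exists to separate a drug effect from expectation, and attribution is where expectation enters most directly. A primary outcome filtered by belief would bring back part of what blinding and placebo are meant to remove.

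A reader who starts from 2.13 will expect an attributed-symptom result. A reader who checks SAP 2.3.8 for departures will conclude that the primary outcome is unchanged. Both would be misled about what is tested.

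**Working it through.** **1. The definitions side by side.**

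| Source | Limited to attributed symptoms? |
|---|---|
| Protocol 2.13, primary outcome | Yes |
| Protocol synopsis | No |
| Protocol 2.13, secondary outcome 1 | No: it takes patients with symptoms and asks what proportion attribute them, so symptoms are not already filtered |
| Protocol 2.17, primary analysis | No |
| Protocol Appendix 5, daily form | No attribution item |
| SAP 1.1, 1.7, 2.3.1 | No |

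The clause in 2.13 is the outlier, within the Protocol as well as against the SAP.

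**2. Can the 2.13 definition be scored?** Not day by day, because the daily form has no attribution item. One day-56 answer covering two months could be applied to all seven daily scores. That is a period-level filter, and 2.13 has no rule for a don't-know answer.

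**3. Is the change declared?** No. SAP 2.3.8 says the primary model differs from the protocol's only in the period effects. It treats attribution solely as an added secondary analysis.

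**4. The plan's own sample size.** With 3 statin and 3 placebo periods per person, the participant effect cancels and n = (2/3) × (s × (1.960 + 1.282)/10)².

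- With s = 30 (rationale paragraph, Protocol 2.3): (2/3) × 9.726² = 63.1, so 64, as stated in Protocol 2.4.
- 64/(1 − 0.40) = 107, as stated. 107 × 1.8 = 193, consistent with 200.
- With s = 25 (simulation paragraph, Protocol 2.3) the result is 44. That mismatch is a separate matter.

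The described simulation adds 10 to each statin period and has no step that removes unattributed symptoms. The sample size therefore also rests on the unrestricted score.

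**5. Could the definitions give different answers?** If a share a of symptom burden is attributed equally in both treatments, the difference scales by a: 10 × 0.2 = 2 mm and 10 × 0.8 = 8 mm.

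A simulation illustrates this. Its assumptions are not in the documents: placebo mean 30, between- and within-participant SD 30, scores cut to 0–100, attribution at random by period, 200 × 0.6 = 120 evaluable, 4,000 runs, and a paired test on person means in place of the mixed model.

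| Nominal effect | Attributed, statin / placebo | All symptoms: difference, rejection | Attributed only: difference, rejection |
|---|---|---|---|
| 10 | 30% / 30% | 7.4, 98.5% | 2.3, 24.1% |
| 10 | 50% / 50% | 7.3, 98.4% | 3.7, 41.3% |
| 10 | 70% / 70% | 7.3, 98.2% | 5.1, 65.0% |
| 10 | 60% / 40% | 7.4, 98.5% | 11.4, 100% |
| 0 | 50% / 50% | 0.0, 5.2% | 0.0, 4.8% |
| 0 | 60% / 40% | 0.0, 5.6% | 7.0, 94.5% |

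The nominal 10 shrinks to about 7.3 because scores are cut at 0 and 100. The last row checks by hand: the mean score after cutting is about 35, and 35 × (0.60 − 0.40) = 7. The restricted outcome can therefore be smaller or larger than the unrestricted one.

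**6. The secondary score nearest to 2.13.** SAP 2.3.2 sets the daily score to zero when the participant believes symptoms are, or does not know whether they are, related to study medication. That keeps only symptoms not blamed on the capsule. SAP 2.3.8 describes the reverse: zero when symptoms are attributed to another cause. The binary outcome in SAP 2.3.2 counts related and don't-know as one, which agrees with 2.3.8.

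**The case against.** The best defence is that an analyst following the SAP has no doubt what to do. SAP 1.1, 1.7 and 2.3.1 name the unrestricted score, SAP 2.3.2 labels the attribution-based score secondary, the SAP is to be finalised before database lock, and Protocol 2.4 commits to one clearly specified primary test. The 2.13 clause may be no more than loose drafting. All of this stands, and it rules out several stronger readings.

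- A reader might infer that the headline endpoint can be chosen after the data are seen. Nothing in the SAP lets the attribution version be promoted.
- A reader might infer that the SAP switched the Protocol's outcome. The Protocol synopsis, 2.17 and Appendix 5 already use the unrestricted score.
- A reader might take the figures above as lost power in the planned test. SAP 2.3.1 applies no attribution filter, so they are not.
- A reader might say that the 2.13 definition cannot be applied at all. It could be, at period level.

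The 60%/40% rows also need a caution. Under intact blinding, with no effect on symptom severity, a systematic difference in attribution would need some other route, such as another side effect revealing the allocation.

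Finally, SAP 2.3.8 says the added analysis appeared in a published protocol paper. That paper is not available here, so how it words the primary outcome is unknown.

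What the defence does not remove is that the protocol's formal outcome section states a different primary outcome and the list of changes is silent on it.

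**Conclusion.** The point holds as a contradictory and undeclared definition of the primary outcome. One clause in Protocol 2.13 conflicts with every other definition, with the data collection form and with the stated analysis, and SAP 2.3.8 does not record that it was set aside. It should be corrected because, if followed, it would score a different outcome that depends on participants' beliefs.

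The practical size is unknown. The scaling of 10 mm to 2–8 mm assumes equal attribution in both treatments at shares that the documents do not supply. The simulation shows that the definitions can disagree, not by how much they would here.

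The opposite directions given for the attribution-based secondary score are a definite error, because the two descriptions keep different sets of symptoms.

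**What to change.** 1. Protocol 2.13: delete the attribution clause, so that the daily VAS for any muscle symptoms is the only primary outcome.
2. SAP 2.3.8: add a line stating that the protocol text carried an attribution limit and that the primary outcome does not apply it.
3. SAP 2.3.2: keep the attribution-based daily score as secondary, but set it to zero when the participant attributes symptoms to another cause, in line with SAP 2.3.8. Handle don't-know as the binary outcome does (counted as related, so the score is kept). State that the single day-56 answer is applied to all seven daily scores of its period.

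The cost is a short protocol amendment, since primary outcome wording changes, and a few SAP lines before database lock. No new data are needed, and the sample size is unaffected because it was built on the unrestricted score.

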2.14 MONITORING

GCP section 5.18.3 states in regard to monitoring, *"The determination of the extent and nature of monitoring should be based on considerations such as the objective, purpose, design, complexity, blinding, size and endpoints of the trial. In general, there is a need for on-site monitoring, before, during, and after the trial; however, in exceptional circumstances the sponsor may determine that central monitoring in conjunction with procedures such as investigators training and meetings, and extensive written guidance can assure appropriate conduct of the trial in accordance with GCP. Statistically controlled sampling may be an acceptable method for selecting the data to be verified."*

StatinWISE is a pragmatic, randomised placebo controlled trial. The intervention (atorvastatin) has marketing authorisation in the United Kingdom and has been in clinical use for decades. The trial will collect data on SAEs which may be associated with this product and other clinical conditions which will be common in this population. These events will be reviewed routinely by the trial Medical Advisor and will be reported routinely to the Trial Steering Committee. The trial involves getting consent, giving the trial drug in the usual way and collecting information regarding muscle symptoms directly from the patients. There are no extra tests or procedures unless patients agree

to take part in the genetic study, for which 9 ml of blood is required. Apart from the trial drug, any other medication will be issued as per usual practice under the care of the GP. For these reasons, we believe that the risk of harm or injury (whether physical, psychological, social or economic) to trial patients is low. We will use central monitoring along with investigators' training and meetings, and extensive written guidance to make sure the trial is carried out properly. Statistically controlled sampling will be used to select data to be verified at GP practices. We plan to carry out on-site monitoring where central statistical monitoring show abnormality. Consent forms will be monitored centrally at the CTU.

Investigators/practices are required to provide direct access to source data/documents for trial-related monitoring, audits, ethics committee review and regulatory inspection. Source data will be low as the majority of patients will enter data using the mobile application method directly. All trial-related and source documents must be kept for ten years after the end of the trial.

